8.4.2. Patients Lost to Follow-Up

A patient would be considered potentially lost to follow-up if he or she repeatedly fails to return for scheduled visits and is unable to be contacted by the study site. Site personnel are expected to make diligent attempts to contact patients who fail to return for a scheduled visit or were otherwise unable to be followed up by the site. Refer to the Retention Guide for additional details. Vital status will be collected within legal and ethical boundaries during the study closeout period. If vital status is determined, the patient will not be considered lost to follow-up.

8.4.3. Discontinuation of Study Sites or the Study

The Sponsor may suspend enrollment or discontinue a site at any time. A written statement will be provided to the Investigator, the IRB or IEC, and regulatory authorities, if required.

Possible reasons for site discontinuation include, but are not limited to:

- Unsatisfactory enrollment with respect to quantity or quality
- Inaccurate or incomplete data collection on a chronic basis
- Falsification of records
- Failure to adhere to the protocol
- Lack of study oversight by the Principal Investigator and/or designee

If any serious or nonserious AEs have occurred at such a clinical site, all documentation relating to the event(s) must be obtained.

The Sponsor in consultation with the Executive Committee (EC) Chair will retain responsibility for discontinuation of the study. The study will be discontinued if necessary for medical, safety, regulatory or other reasons consistent with applicable laws, regulations, and Good Clinical Practice (GCP).

Discontinuation of the study may be based on a recommendation from the DMC. The criteria that the DMC will follow to recommend early termination the study will be described in the DMC Charter.

8.5. Overdose

There is no specific antidote for an overdose of bempedoic acid. Management of an overdose should be focused on the treatment of symptoms. These symptoms should be managed according to current standards of care with appropriate supportive measures. Also discontinuation of study drug should be considered, based on medical judgement.

9. ASSESSMENT OF EFFICACY

9.1. Efficacy Parameters

After randomization, patients will return to clinic/or have phone contact with the clinic every 4 to 12 weeks for a total of 24 weeks. Clinical laboratory samples will be collected and analyzed for basic lipid parameters at each visit.

[figure not shown]
9.2. Clinical Efficacy Laboratory Tests

Blood draws for efficacy (not safety) must meet the criteria below. If these criteria have not been met, efficacy blood samples will NOT be collected. **If these criteria can be met by rescheduling the clinic visit (within 3 days), efficacy blood samples will be collected at the rescheduled clinic visit only.**

- Blood samples will be drawn after a minimum 10-hour fast (water is allowed), and
- Patients will be in a seated position during the blood collection. Clinical laboratory parameters and tests will include those listed in [Table 3](#). Collection schedule and instructions are provided in the Clinical Laboratory Manual. A description of the sample collection, storage, and shipping as well as monitoring and management of abnormal laboratories are described in [Section 10.1.6](#).

When ECG, vital signs, and laboratory samples are to be collected at the same time point, ECG and vital sign measurements will precede laboratory sample collection.

Table 3: Clinical Efficacy Laboratory Tests

Clinical Laboratory Test	Clinical Laboratory Test
Basic Lipid Parameters 
• Total cholesterol (TC)• low-density lipoprotein cholesterol (LDL-C) and non-HDL-C 	Other Parameters 
• High-sensitivity C-reactive protein (hs-CRP)• Apolipoprotein B (apoB)

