8.3.7. Treatment Week 12 (Visit T4; Day 85 ±3 days)

Patients will undergo the following assessments and procedures at Week 12 (Visit T4):

1. Concomitant medication review (ongoing)
2. Assess AEs, SAEs, and potential clinical endpoints (ongoing)
3. Weight
4. Vital signs
5. Central clinical laboratory evaluations:
 - Hematology, blood chemistry, and urinalysis
 - apoB
 - hs-CRP
 - HbA_{1C}
 - Basic fasting lipids (TC, calculated LDL-C, HDL-C, non-HDL-C, and TG)
 - PK Sample before dose

6. Diet and exercise counseling
7. Return of study drug; assessment and recording of dosing adherence
8. IWRS contact to obtain new MED ID numbers for double-blind study drug
9. Dispense double-blind study drug and provide dosing instruction

Note: If the patient discontinues at any scheduled visit after T1, or between study visits, please proceed to [Section 8.4.1](#) for detailed instructions.

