8.3.8. Treatment Week 24/EOS (Visit T5; Day 169 ±7 days)

Patients will undergo the following assessments and procedures at Week 24 (Visit T5):

1. Concomitant medication review (ongoing)
2. Assess AEs, SAEs, and potential clinical endpoints (ongoing)
3. Weight
4. Vital signs
5. Central clinical laboratory evaluations:
 - Hematology, blood chemistry, and urinalysis
 - apoB
 - hs-CRP
 - HbA_{1C}
 - Basic fasting lipids (TC, calculated LDL-C, HDL-C, non-HDL-C, and TG)
 - PK Sample before dose
6. Return of study drug; assessment and recording of dosing adherence
7. IWRS contact to terminate the subject or register completion
8. Physical Exam
9. 12-Lead ECG

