8.4.1. Procedures for Early Withdrawal

If a patient withdraws or is removed from the study for any reason, all "End of Study" procedures should be completed. Reason for withdrawal, date of the discontinuation, and date of the last dose of study drug should be recorded in the appropriate section of the eCRF.

Additionally, the discontinuation visit date must be registered in IWRS. Study drug assigned to the withdrawn patient may not be assigned to another patient.

All effort should be made to have each patient complete all study visits on schedule according to the protocol. Accommodations for early or late visits in special circumstances will be considered by the Sponsor to prevent early withdrawal. Written notice (regardless of cause) is to be provided within 48 hours of the withdrawal to the Sponsor personnel or the Medical Monitor. At the time of discontinuation, every effort should be made to ensure all relevant procedures and evaluations scheduled for the final study visit are performed.

Patients choosing to withdraw from the study early should be encouraged to return for all study scheduled clinic visits even if they are no longer taking IMP. Patients who withdraw from all aspects of the study will be asked to consent to clinical visits or phone calls for safety assessments, including AEs, concomitant medication, and current health status through Week 24 (Visit T5). Subjects who are unwilling to return for clinic visits should return for an end of study visit (Visit T5).

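### Protocol 9.2 allows only 3 days to reschedule a fasted efficacy draw, so a Week 12 value that the SAP could still assign to that visit may be imputed instead

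*Protocol*

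**What the plan says.** **Protocol 9.2** sets conditions for efficacy draws only: "Blood draws for efficacy (not safety) must meet the criteria below". The patient must be seated, and "Blood samples will be drawn after a minimum 10-hour fast". Otherwise, "If these criteria have not been met, efficacy blood samples will NOT be collected". The one remedy is this: "If these criteria can be met by rescheduling the clinic visit (within 3 days), efficacy blood samples will be collected", and then at that rescheduled visit only. Nothing is said about a patient who cannot return fasted within 3 days. Table 3 lists the efficacy tests as TC, LDL-C, non-HDL-C, hs-CRP and apoB.

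**Visit timing.** Week 12 (Visit T4) is Day 85 ±3 and Week 24 (Visit T5) is Day 169 ±7 (Protocol 8.3.7 and 8.3.8). Section 8.4.1 adds: "Accommodations for early or late visits in special circumstances will be considered by the Sponsor to prevent early withdrawal".

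**SAP 6.4** has a row of eight visit windows. The seventh is Days 72 to 127, and the eighth starts at Day 128 and has no upper bound. The column headings, and the text of 6.3 on retests and unscheduled visits, are missing from the copy reviewed.

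**SAP 18.1.3 and Appendix 4** impute a missing Week 12 value by regression. For patients still on treatment the model contains treatment, stratum and baseline. For bempedoic acid patients off treatment it contains stratum and baseline and is fitted to placebo data.

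**The concern.** An unfasted visit does not make the value unobtainable. A patient who continues treatment receives a second bottle at T4, so a fasted sample taken a week or two later still measures LDL-C on study drug. Section 9.2 makes no provision for that sample once 3 days have passed, and the value becomes missing by rule.

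One such visit removes several endpoints together: the primary endpoint and four of the five key secondaries (Week 12 non-HDL-C, TC, apoB and hs-CRP). What is at stake is precision and the number of primary values that rest on a model instead of a measurement.

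Three days may also be hard to meet for users of a PCSK9 inhibitor. Inclusion criterion 4 requires their lipids to be drawn before the injection and no more than 48 hours before it. Any redraw has to satisfy that rule as well.

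**Working it through.** **1. Which SAP window is Week 12?** The headings are lost, so the cut-points are checked against midpoints of the scheduled days (29, 57, 85 and 169 for T2 to T5):

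- T2/T3: (29 + 57)/2 = 43
- T3/T4: (57 + 85)/2 = 71
- T4/T5: (85 + 169)/2 = 127

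The SAP windows end at 43, 71 and 127, an exact match. Days 72 to 127 are therefore Week 12.

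**2. Latest Week 12 draw under 9.2.** The T4 window closes at Day 85 + 3 = 88. If the 3-day reschedule runs from a Day 88 visit, the limit is Day 88 + 3 = 91. The SAP window stays open for 127 − 91 = 36 or 127 − 88 = 39 further days. Day 127 is (127 − 1)/7 = 18 weeks after Day 1.

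**3. What imputation gives back.** The primary ANCOVA (SAP 18.1.2) adjusts for treatment, patient type and baseline. The imputation model for patients on treatment holds the same three terms. LDL-C is measured at Week 4 but is not used. With no predictor beyond those in the analysis model, imputation restores little information. If a fraction f of values is lost evenly across arms, the standard error rises by roughly 1/√(1 − f) − 1.

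**4. Size.** The documents give no rate of unfasted visits that cannot be repeated within 3 days, so f is an assumption:

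| Assumed f | Values lost of 300 | Rise in SE and CI width |
|---|---|---|
| 1% | 3 | 0.5% |
| 2% | 6 | 1.0% |
| 5% | 15 | 2.6% |
| 10% | 30 | 5.4% |

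**5. Power.** The public text gives no effect size or SD, so the plan's own power cannot be reproduced. For illustration, power = Φ(δ/SE − 1.96), with SE = SD × √(1/n₁ + 1/n₂), for 200:100 patients and for 190:95 (f = 5%):

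| Assumed δ / SD (percentage points) | No loss | f = 5% |
|---|---|---|
| 5 / 15 | 77.7% | 75.6% |
| 8 / 20 | 90.4% | 88.9% |
| 10 / 20 | 98.3% | 97.8% |
| 15 / 25 | 99.8% | 99.8% |

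**The case against.** The strongest reply is that fasting is part of how the endpoint is measured. The primary variable is a calculated LDL-C from a fasting lipid panel. A reader might infer that 9.2 is wrong to refuse the unfasted sample, or that unfasted tubes should be drawn and direct LDL-C measured instead. The documents do not support that. Refusing a non-conforming sample is legitimate, and SAP 18.1.1 calls for measured LDL only when TG exceeds 400 mg/dL or LDL-C is 50 mg/dL or below. This part of the objection stands in full.

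Second, the SAP window assigns collected data to visits; it does not authorise collection. A wide analysis window around a ±3-day visit is no contradiction, and a Day 127 sample is a poor Week 12 value. This also stands, and it is why a redraw should be early. Nor can it be said that any late sample would be fully usable. The retest text is missing, and the on-treatment and adjunctive-therapy sensitivity analyses (SAP 18.2.3) would drop some late values.

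Third, a reader might infer bias, with off-drug bempedoic acid patients imputed as if on placebo because 9.2 withheld their blood. The documents do not establish this. Protocol 8.4 and the note to Table 2 class basic lipids in off-drug patients as safety assessments, and 9.2 governs efficacy draws only, so it may not reach their LDL-C. The same note leaves out apoB and hs-CRP for them. Patients still on drug are imputed from their own arm.

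Fourth, 8.4.1 allows for late visits. Its stated purpose is to prevent early withdrawal, so it does not clearly cover a patient who stays in the study and merely arrived unfasted.

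**Conclusion.** The point holds as a cheap improvement, not as a flaw that threatens the trial. Followed as written, 9.2 can turn an obtainable primary value into an imputed one, although a fasted sample taken later would fall in the SAP's Week 12 window. At an assumed 2% to 5% of patients, 6 to 15 primary values are lost and the interval widens by about 1.0% to 2.6%. In the illustrative scenarios, power falls by about 2 points at most at 5% loss.

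This rests on three things: the assumed rate, the reading of the SAP window from visit midpoints, and the missing text of SAP 6.3 and 6.4 not excluding a late redraw. No claim of bias is made.

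**What to change.** Amend Protocol 9.2 and the laboratory manual as follows:

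- Keep the bar on unfasted efficacy draws. If a fasted visit within 3 days is not possible, take the fasted efficacy draw as soon as possible afterwards, within the SAP Week 12 window, and record the actual day.
- Set a separate limit for Week 24. Study drug is returned at T5 and the SAP window has no upper bound, so a late redraw there could measure LDL-C off drug.
- State whether 9.2 applies to patients off study drug, whose basic lipids are classed elsewhere in the protocol as safety assessments.
- Confirm in SAP 6.3 and 6.4 how such a redraw is selected for analysis.

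The cost is wording, plus a few Week 12 values drawn later than Day 91.

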10. ASSESSMENT OF SAFETY

10.1. Safety Parameters

At all clinic visits, investigators will review all safety information including vital signs, AEs, concomitant medications, and ECG reports and will ensure that the collected data are recorded into the appropriate eCRF. Additionally, clinical laboratory samples will be collected and sent for analysis and the investigator will review the results to ensure continued patient safety while participating in the study.

10.1.1. Demographic/Medical History

Demographic data and a complete medical history will be obtained from the patient. For medical history, conditions that are relevant and/or clinically significant should be captured with at least a start date (month and year) and whether the condition is ongoing or resolved. All surgeries regardless of date should be reported.

10.1.2. Vital Signs

Vital signs will include DBP and SBP as well as heart rate.

The patient should sit quietly for 5 minutes prior to collection of vital signs. At all time points, vitals will be collected prior to blood collection. Blood pressure and heart rate will be measured using a calibrated, fully automated machine with a cuff that is appropriate to the size of the upper arm. If a fully automated machine is not available, BP may be measured manually. The same method (either automated or manual) and the same arm (right or left) must be used throughout the study. The patient should be in a seated position with feet touching the floor. Patients should be seated quietly for at least 5 minutes in a chair with their backs supported, their feet flat on the ground, and their arms bared and supported at heart level. At each clinic visit, 2 BP measurements will be collected at least 5 minutes apart.

10.1.3. Weight, Height, and Body Mass Index

Weight will be measured on a calibrated scale while fasted, using consistent scales, after voiding, and without shoes and outerwear (eg, coats).

Height will be measured using standard clinic procedures.

BMI will be calculated using the formula:

$$\text{BMI (kg/m}^2\text{)} = \text{weight in kg} / (\text{height in meters})^2$$

10.1.4. Physical Examination

PEs will include an assessment of the following:

- General appearance
- Skin
- Eyes, ears, nose, and throat
- Head and neck
- Extremities
- Musculoskeletal examination
- Respiratory examination
- Cardiovascular assessment, including rhythm and presence of cardiac abnormalities
- Abdominal examination
- Neurologic examination including documentation of the presence of abnormalities in mental status and motor and sensory function
- Any additional assessments necessary to establish baseline status or evaluate symptoms or adverse experiences

Documentation of the PE findings will be included in the source documentation at the clinical site. Significant findings noted at Visit S2 will be recorded on the Medical History/Current Medical Conditions page of the eCRF. Only changes from Visit S2 physical examination findings (or other unscheduled physical exams performed after informed consent but prior to randomization) that meet the definition of an AE will be recorded on the AE page of the eCRF.

Note: Additional information will be collected regarding muscle-related AEs. See [Section 10.2.11.3.3](#).

10.1.5. Electrocardiogram

ECG collection will be preceded by a 10-minute rest time during which the patient will remain in the supine position. ECGs will be collected prior to blood collection. ECGs will be assessed using machine readings and physician review.

10.1.5.1. Monitoring and Management of Abnormal Electrocardiograms

If a clinically significant ECG abnormality not present at baseline (screening) is determined by the Investigator to be related to study drug, the abnormality will be discussed with the Sponsor personnel or the authorized Medical Monitor, and followed and evaluated with additional tests (if necessary) until the underlying cause is determined or the event is brought to an acceptable resolution. Additional clinical and laboratory information will be collected and carefully documented in order to better characterize the ECG abnormality and rule out alternative causes. ECG findings determined to be a clinically significant change from baseline should be reported as an AE regardless of causality.

Unscheduled ECG assessments will be completed at the discretion of the Investigator.

10.1.6. Clinical Laboratory Tests

10.1.6.1. Laboratory Parameters (Safety)

Patients will be in a seated position during the blood collection. Clinical laboratory parameters and tests will include those listed in [Table 3-Table 4](#). Collection schedule, schedule of laboratory parameters by visit, and instructions are in the Clinical Laboratory Manual provided by Central Laboratory.

Table 4: Clinical Laboratory Parameters (Safety)

Clinical Laboratory Test	Clinical Laboratory Test

Hematology
 
 • Hematocrit (Hct) • Hemoglobin (Hgb) • Mean corpuscular hemoglobin (MCH) • Mean corpuscular hemoglobin concentration (MCHC) • Mean corpuscular volume (MCV) • Platelet count • Red blood (RBC) cell count • White blood (WBC) cell count with differential (absolute and %) 	
Blood Chemistry (serum, fasting)
 
 • Albumin (Alb) • Alkaline phosphatase (Alk-P) • Alanine aminotransferase (ALT; SGPT) • Aspartate aminotransferase (AST; SGOT) • Blood urea nitrogen (BUN) • Calcium (Ca) • Carbon dioxide (CO₂) • Chloride (Cl) • Creatinine • Creatine kinase (CK) • Glucose • Lactate dehydrogenase (LDH) • Phosphorus • Potassium (K) • Sodium (Na) • Total and direct bilirubin (TB) • Total protein • Uric acid

Urinalysis (Dipstick)
 
 • Clarity • Bilirubin • Color • Glucose • Ketones • Leukocyte esterase • Nitrite • Occult blood • pH • Protein • Specific gravity • Urobilinogen • Urine Pregnancy in females of child bearing potential 	

Table 4: Clinical Laboratory Parameters (Safety)

Clinical Laboratory Test	Clinical Laboratory Test

Urinalysis (Microscopic)-only if urine dipstick abnormal
 
 • Bacteria • Casts • Crystals • Epithelial cells • Red blood cell (RBC) • WBC 	
Coagulation – all patients at Visit S1; only in patients receiving vitamin K antagonists at Visit T1 and 3 to 5 days post Visit T1 using local or central lab
 
 • Prothrombin time (PT) • International normalized ratio (INR)

Other Screening Labs
 
 • Hepatitis B surface antigen (HBsAg), hepatitis C virus (HCV) • Serum pregnancy test (only for females of childbearing potential) • Follicle-stimulating hormone (FSH; Females <55 years and >1 year without menses) • Thyroid-stimulating hormone (TSH) 	
Additional samples
 
 • Hemoglobin A_{1C} (HbA_{1C})

10.1.6.2. Clinical Laboratory Tests (PK)

A PK blood sample will be collected prior to dosing at Visits T2, T4, and T5.

Patients will be in a seated position during the blood collection. Collection schedule and instructions are provided in the Clinical Laboratory Manual. A description of the sample collection, storage, and shipping are described in [Section 10.1.6.3](#).

10.1.6.3. Sample Collection, Storage, and Shipping

Clinical laboratory and PK samples will be collected by appropriate clinical site personnel and then shipped according to a separate laboratory manual provided by the Central Laboratory. Samples will be processed by the Central Laboratory, and PK samples will be forwarded to the Bioanalytical Laboratory for analysis.

10.1.6.4. General Monitoring and Management of Abnormal Clinical Labs

It is the Investigator’s responsibility to review the results of all laboratory tests as they become available and to sign and date the report to document their review. For each laboratory test outside of the laboratory normal range, the Investigator needs to ascertain if this is a clinically significant change from baseline for the individual patient, with baseline defined as the last value or observation before the first dose of study drug. The Investigator may repeat the laboratory test or request additional tests to verify the results of the original laboratory test.

If a laboratory value is determined to be an abnormal and clinically significant change from baseline for the patient, the Investigator should determine if it qualifies as an AE, and if yes, an appropriate eCRF will be completed. An abnormal laboratory value that is not already associated with an AE is to be recorded as an AE only if any one of the following criteria is met:

- An action on the study drug is made as a result of the abnormality.
- Intervention for management of the abnormality is required.
- At the discretion of the investigator should the abnormality be deemed clinically significant.

All clinically significant laboratory abnormalities occurring during the study that were not present at baseline should be followed and evaluated with additional tests if necessary, until diagnosis of the underlying cause or resolution. Adverse events of special interest (AESI) monitored by clinical laboratories are discussed in the section on AESI ([Section 10.2.11](#)).

10.1.6.5. Total Blood Volume of Clinical Laboratory Samples

The total number of venipunctures and total volume of whole blood collected during the study will be limited to that needed for safety monitoring, efficacy, biomarker assessment, and genetic analysis. Total whole blood volume collected over the study duration is not to exceed approximately 250 mL for each patient.

10.2. Adverse and Serious Adverse Events

10.2.1. Definition of Adverse Event

An AE is any untoward medical occurrence in a clinical investigation patient administered a pharmaceutical product, including control, and which does not necessarily have a causal relationship with treatment.

An AE can be:

- Any unfavorable and unintended sign (including an abnormal laboratory finding), symptom, or disease temporally associated with the use of a medicinal product, whether or not considered related to the medicinal product
- Any new disease or exacerbation of an existing disease
- Any deterioration in nonprotocol-required measurements of laboratory value or other clinical test (eg, ECG or x-ray) that results in symptoms, a change in treatment, or discontinuation from study drug
- TEAEs are defined as AEs that begin or worsen after the first dose of study drug
- Adverse drug reaction (ADR; see [Section 10.2.2](#))

